STUDY PROTOCOL

TITLE: AROMATHERAPY AS AN ADJUNCTIVE THERAPY FOR NEONATAL ABSTINENCE SYNDROME

NCT: 03097484

ADDRESS: DEPARTMENT OF PEDIATRICS
DIVISION OF NEONATOLOGY
UNIVERSITY OF KENTUCKY
[name]
[name]

FUNDING: DIVISION OF NEONATOLOGY

ABBREVIATIONS: NAS, NEONATAL ABSTINENCE SYNDROME

DOCUMENT DATE: MARCH 27, 2019

STUDY BACKGROUND

The United States, Appalachia, Eastern Kentucky in particular, is in the midst of a major opioid abuse epidemic. This current epidemic is driven by misuse of prescription painkillers, i.e. Subutex and Saboxone. As prescription pills become more expensive and harder to acquire, addicts are seeking similar, cheaper drugs; such as heroin. From 1998 to 2011, the prevalence of opioid abuse and dependence amongst pregnant women has increased by 127%, from 1.7 per 1000 to 3.9 per 1000. Neonatal Abstinence Syndrome (NAS) or neonatal opioid withdrawal syndrome is a condition produces gastrointestinal and autonomic neurologic dysfunction. Infants with severe withdrawal experience dysregulation of autonomic functions, resulting in feeding difficulty, diarrhea, excessive sleepiness, and tremors. Nearly two thirds of all babies exposed to opioids during gestation will require admission to a neonatal intensive care unit for management of withdrawal symptoms. During a typical year the Neonatal Intensive Care Unit (NICU) at Kentucky Children's Hospital admits approximately 100-120 infants exhibiting NAS symptoms; these infants have a typical length of stay of 24 days if they require pharmacologic treatment.

The mainstay of treatment for NAS involves opioid replacement therapy with morphine to minimize withdrawal symptoms. Once symptoms are well controlled, the infant is said to have been "captured." At this point a slow weaning of his morphine dose occurs. The infants' clinical status is assessed with the Finnegan Scoring system, which examines symptoms such as crying, excessive sleepiness or difficulty sleeping, insomnia, or tremors along with objective findings such as temperature and respiratory rate.

In addition to pharmacotherapy, alternative and complementary medicine techniques are slowly entering the NAS treatment algorithm. Treatments such as music therapy infant massage, kangaroo care, aromatherapy, and acupressure are now employed in NICUs in addition to traditional opioids replacement. However, few studies exist in the literature to evaluate their effectiveness.

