Aromatherapy is the practice of using natural essential oils to achieve a desired effect in an individual. Scents such as lavender and chamomile have been documented to have a soothing calming effect. Studies involving infants shown that lavender not only reduce crying and enhance sleep, but also reduce levels of salivary cortisol, a stress hormone. Additionally, aromatherapy is currently used as an adjunctive therapy at the University of Kentucky's Markey Cancer Center.

Salivary cortisol is a non-invasive biomarker that has proven useful for monitoring stress in neonates. It is a simple and painless method for monitoring the stress hormone cortisol. Salivary cortisol has been used successfully in infants as a method to assess infant stress associated with prone position versus supine positioning. These studies have shown that salivary cortisol levels vary with stressful or soothing stimuli.

To date, no dangerous or deleterious effects have been described from traditional inhalational use of aromatherapy or with salivary cortisol sampling. Studies have shown aromatherapy to be an effective adjunctive therapy by proving a calming effect. In our patient population it may prove to be a useful complimentary therapy ultimately reducing infant stress, hospital length of stay, and burden of opioid use. Additionally, salivary cortisol's ease of collection and non-invasive nature make it an ideal biomarker to study.

INCLUSION/EXCLUSION CRITERIA

Inclusion Criteria:

- Infants greater than or equal to 36 weeks EGA
- Intrauterine opioid exposure
- Primary diagnosis of NAS
- Parental permission to participate

Exclusion Criteria:

- Infants less than 36 weeks EGA
- Major congenital anomalies
- Latrogenic drug withdrawal
- Diagnosis of infection or respiratory distress
- Prior initiation of opioid replacement therapy
- Non-English speaking
- Infants with respiratory conditions

ENROLLMENT

Patients will be evaluated at admission or transfer to the University of Kentucky NICU and consent obtained from the mother. Patients will be randomized to one of two groups using block randomization in groups of four. The study will not be blinded (open-label).

STANDARD OF CARE AND INTERVENTION

Standard of care will include quiet environment, occupational therapy, music therapy and infant massage. Kangaroo care and breast feeding will be encouraged based on clinical recommendations.

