Interventional treatment will include all aspects of the standard of care in addition to aromatherapy. Patches will be obtained from BioEsse Technologies™ and will have an 80:20 mixture of Lavender and Chamomile in a 55-microliter standard dose. When activated, each patch releases, the mixture over a 2-8 hour period by design and a

constant diffusion rate. These will be attached to a positioning device placed in the infant's bassinet 6-8 inches from the infant's nose for a period of 4 hours twice a day.

ASSESSMENT

Comfort levels will be assessed using the MOTHER-NAS scoring system. After three consecutive scores of greater than or equal to 9 or two consecutive scores of greater than or equal to 13, replacement morphine (0.05mg/kg/dose every three hours) will be initiated. After 48 hours of symptom control, morphine will be weaned by 0.02mg/day. Any significant increase in scores that accompanied the wean will induce a return to the previous dose.

DATA COLLECTION AND STATISTICAL ANALYSIS PLAN

Data will be collected from hospital electronic medical records and stored in a secure manner. Data will include: 1) date of birth, 2) date of admission, 3) birth weight, 4) gender, 5) APGAR scores, 6) mode of delivery, 7) place of birth, 8) type of prenatal drug exposure, 9) prenatal care, 10) Finnegan scores, 11) average daily heart rate, 12) daily morphine dose, 13) total morphine dose per day, 14) length of treatment, and 15) length of hospitalization.

Data will be analyzed using standard statistical techniques. The two treatment groups will be compared with a two-tailed t-test, while dichotomous variables will be examined with a Chi-Square test. Statistical significance will be set at $p=0.05$.

Anticipated CONSORT Diagram showing the flow of participants through each stage of the trial.

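### No primary outcome, testing order or multiplicity rule goes with the single unadjusted p=0.05, so more than one tested measure takes the false-positive chance above 5% (illustratively 10-26%)

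*Combined protocol and SAP*

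**What the plan says.** The section DATA COLLECTION AND STATISTICAL ANALYSIS PLAN gives the tests in one sentence: "The two treatment groups will be compared with a two-tailed t-test, while dichotomous variables will be examined with a Chi-Square test". The next sentence sets the level: "Statistical significance will be set at $p=0.05".

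The same section lists fifteen data items. The first nine are baseline or descriptive. The rest are observed after randomisation: "10) Finnegan scores, 11) average daily heart rate, 12) daily morphine dose, 13) total morphine dose per day, 14) length of treatment", followed by "15) length of hospitalization". That makes six measures, or five if items 12 and 13 are the same quantity, which their wording allows. The list is of data to collect. It does not mark any item as an outcome or say which items will be compared between groups.

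There is no section on objectives or hypotheses. The nearest text is a sentence in STUDY BACKGROUND that hopes the therapy may help by "ultimately reducing infant stress, hospital length of stay, and burden of opioid use". Three effects are mentioned there, and none is ranked above the others.

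**The concern.** A 5% level describes the error rate of one pre-specified test. When several measures are available and none is designated, a significant result on any of them can be presented as evidence that aromatherapy works, and the chance of at least one such result under no effect exceeds 5%. The trial is also open-label, so pre-specification is one of the few safeguards against selecting the favourable result. A nominally significant difference in, say, heart rate or length of stay could not then be read at its stated error rate.

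**Working it through.** **The plan's own figure.** The document gives no familywise error rate, power or sample size, so there is no design figure to reproduce.

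**Inputs from the document.** Two-sided 0.05 per test, and items 10-15 as candidate measures (k = 6, or k = 5 if items 12 and 13 are one). The three hoped-for effects in STUDY BACKGROUND give k = 3.

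**Assumed inputs.** Each measure is tested exactly once, there is no true effect on any, and the test statistics are jointly normal with correlations that the document does not give. For k = 3, Finnegan scores stand in for stress. The background text presents salivary cortisol as the stress marker, but cortisol is not in the data list. Cortisol and any Chi-Square comparisons are not counted.

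**Independent tests.** P(at least one false positive) = 1 − 0.95^k.

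- k = 6: 1 − 0.95^6 = 0.265
- k = 5: 1 − 0.95^5 = 0.226
- k = 3: 1 − 0.95^3 = 0.143

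**Equal correlation ρ.** With c = 1.960,

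P = 1 − ∫ φ(u) [Φ((c − √ρ·u)/√(1−ρ)) − Φ((−c − √ρ·u)/√(1−ρ))]^k du,

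evaluated by numerical integration:

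| k | ρ=0 | 0.3 | 0.5 | 0.7 | 0.9 | 0.95 |
|---|---|---|---|---|---|---|
| 6 | 26.5% | 24.1% | 20.7% | 16.4% | 10.8% | 8.9% |
| 5 | 22.6% | 20.9% | 18.3% | 14.8% | 10.2% | 8.5% |
| 3 | 14.3% | 13.6% | 12.5% | 10.9% | 8.4% | 7.3% |
| 2 | 9.8% | 9.5% | 9.1% | 8.4% | 7.0% | 6.5% |

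Simulated two-sample t-tests (an assumed 20 infants per arm, 20,000 replicates) agree at ρ = 0, 0.5 and 0.9: 26.6%, 20.6% and 10.9% for k = 6, and 23.0%, 18.2% and 9.9% for k = 5.

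**Unequal correlations.** The document gives reason to expect positive correlation. In ASSESSMENT, scores drive the start of morphine and its wean: "Any significant increase in scores that accompanied the wean will induce a return to the previous dose". STUDY BACKGROUND ties stay to drug treatment: "these infants have a typical length of stay of 24 days if they require pharmacologic treatment". I therefore assumed 0.7-0.9 among dose, treatment length and stay, 0.3-0.7 between scores and those, and 0-0.5 between heart rate and everything else. For k = 6 a second dose item joins the first group. Simulation (4,000,000 draws per setting), from the high-correlation end to the low:

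- k = 5: 14.4% to 19.2%
- k = 6: 15.1% to 21.1%
- k = 3 (scores, stay, dose): 10.0% to 12.6%

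**What the independence values bound.** For jointly normal two-sided statistics, the values at ρ = 0 are the maximum over all correlations, but only if each measure is tested once. With no assumption about dependence, the Bonferroni bound is 5 × 0.05 = 25% for five tests and 6 × 0.05 = 30% for six. Scores, heart rate and dose are recorded repeatedly with no per-infant summary defined, so day-by-day testing could exceed all of these figures.

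**Check of the remedy.** One primary plus five others, all null, 1,000,000 draws, at ρ = 0, 0.3, 0.5, 0.7, 0.9 and 0.95. If the primary is tested at 0.05 and Holm is applied to the others regardless of its result, the overall rate is 9.6%, 9.1%, 8.2%, 6.9%, 5.4% and 5.1%. If Holm is applied only after a significant primary, it is 5.0% throughout, because no claim is possible without the primary.

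**The case against.** The strongest reply is that both drivers of the percentages are assumed. The plan lists data to collect, not hypotheses to test, and it gives no correlations. If only one measure were tested, there would be no inflation. This stands as a limit on the figures. It does not remove the gap, because two tests already give 7.0-9.8% for correlations from 0.9 to 0, and nothing in the document confines the analysis to one.

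A second reply is that the background language is tentative and the plan states no rule for declaring success, so the results may be meant as exploratory, where unadjusted p-values are accepted practice. That is fair, and labelling the results so would go far to answer the point. But the document does not declare the study exploratory, and it sets a significance threshold without qualification.

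A reader might also treat the three hoped-for effects as formal study aims. The document does not support that: they appear in one background sentence, and the k = 3 calculation needs a stand-in for stress.

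**Conclusion.** The point holds. The plan sets one unadjusted level and names no primary outcome, testing order or multiplicity rule, although five or six post-randomisation measures are available. That defect can be read directly from the text and should be corrected.

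The size is illustrative. If each of the five or six measures is tested once, the chance of at least one false positive is about 14-21% under plausible unequal correlations, 22.6% or 26.5% under independence, and 10-11% at correlation 0.9. One test per hoped-for effect gives about 10-13% under the unequal correlations.

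Two stronger readings should be resisted. One is that the trial has a 26% false-positive rate; 26.5% is the exact value for six independent tests, and the document commits to neither six tests nor independence. The other is that 26.5% is a ceiling; it is one only for jointly normal two-sided statistics with one test per measure, a condition that the undefined handling of the repeated series leaves open.

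**What to change.** Before analysis, add to the statistical section:

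1. One primary outcome with one value per randomised infant, tested at two-sided 0.05. The choice is the sponsor's; length of hospitalization is one example.
2. A statement that all other outcomes are exploratory or, if claims on them are wanted, that they are tested with Holm only if the primary is significant.
3. For each repeated series that is tested (scores, heart rate, morphine dose), one pre-specified per-infant summary or one mixed model with a random infant effect, so that each series yields one test.

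The document is dated March 27, 2019 and gives no recruitment or analysis status. If data have already been seen, the report should disclose that the primary was chosen post hoc.

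The cost is a few sentences of wording, with no change to data collection or treatment. The downside is that non-primary outcomes carry no confirmatory claim, or only a stricter one.
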